COMIRB Protocol

COLORADO MULTIPLE INSTITUTIONAL REVIEW BOARD [name] [contact] [contact]

Protocol #:	20-2772
Project Title:	Discontinuation of Disease Modifying Therapies (DMTs) in Multiple Sclerosis (MS): Extension of the DISCOMS Study
Principal Investigator:	[name]
Version Date:	12Aug2021

I. Hypotheses and Specific Aims:

Main hypothesis: The DISCOntinuation of disease modifying therapies (DMTs) in Multiple Sclerosis (MS-DISCOMS) study is a maximum two-year, randomized controlled clinical trial (RCT) assessing whether relatively older (55+), stable (no relapse for 5+ years, no new magnetic resonance imaging abnormalities of the brain or spine for 3+ years) MS patients who discontinue their DMT have no greater recurrence of disease activity compared to those who continue use of their DMT. We propose an extension of this trial in a 100-person subset of those from the original study who remain in their original drug assignment group at the end of the primary DISCOMS trial in order to continue to assess the duration of follow-up to more fully answer the question of the duration of safe withdrawal if that is the case. To date, the DSMB has not stopped the study, and the final participants have not completed the trial as yet. Thus, we have no new information on the equipoise of the original hypothesis. The **Main Hypothesis of this extension trial** is that among those who have successfully discontinued their DMT as part of the DISCOMS trial (i.e. did not have a new MS relapse or brain MRI lesion) and remain off DMT after DISCOMS are at no greater risk of new or worsened MS disease activity compared to those who successfully continued their DMT as part of DISCOMS and remain on DMT, each assessed at least one year after termination of the primary DISCOMS study.

Specific Aims:

In MS patients who participated in the primary DISCOMS trial, successfully completed a minimum of 18 months of the two year primary DISCOMS study and remained in their original assignment group (i.e. either have discontinued or continued their DMT or another DMT), we will compare clinically significant and patient-relevant outcomes in those who have persistently discontinued vs persistently continued DMTs to determine if:

- 1. Risk of new relapses or brain MRI lesions is no worse in those persistently discontinuing
- 2. Risk of disability progression (by the Extended Disability Status Scale EDSS) is no worse in those persistently discontinuing

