What is the main reason you participated in the DISCOMS extension study? Please circle one.

a) To possibly stop my MS medication, b) Increased access to doctor, nurse, and study team, c) Increased monitoring of my disease, ex. more frequent MRI, d) Possibility of saving money by going off my MS medication, e) Participation in clinical research to further medical knowledge of MS, f) Other: Please list other reason(s)

What is the main reason you stayed in the extension study? Please circle one.

a) To possibly stop my MS medication, b) Increased access to doctor, nurse, and study team, c) Increased monitoring of my disease, ex. more frequent MRI, d) Participation in clinical research to further medical knowledge of MS, e) Other: Please list other reason(s)

B. Description of Population to be Enrolled:

Inclusion criteria:

- Participation in and completion of the DISCOMS trial (NCT# 03073603) for a minimum of 18 and maximum of 24 months (i.e., it is possible some will have been enrolled late enough in the primary study so as to not have completed the full 24 months).
 - Only include participants in the following study groups:
 - Randomized to the discontinue group, stayed off their DMT throughout and after the trial
 - Randomized to the continue group, continuously* stayed on their DMT throughout and after the trial
- Must be willing to continue in their previously-assigned treatment group for the entire, additional 12-Month follow-up period. For those in the continue group, the participant may have switched to a generic or biosimilar version of their medication, or to a different approved medication, if due to intolerance, convenience or insurance mandates, but NOT if due to having new or worsening MS disease activity.
- RRMS, SPMS, or PPMS by McDonald 2010 criteria⁹. Patients will be defined by subtype based on 2013 updated phenotypic criteria¹⁶. Progression of MS will be defined by the local principal investigator either prospectively with an EDSS change of at least 1.0 points over the last two years, or retrospectively, with any significant change in motor function over at least one year, unrelated to relapse.

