It is possible that data from the primary DISCOMS trial will become available before the end of participation by those in the extension trial. Whatever the outcome: if the data will conclude that those who have discontinued DMT have an inferior outcome compared to those who continued DMT or if the trial concludes there is no evidence of a difference to date, all participants still in the extension trial will be given results of the primary DISCOMS study by telephone, or email if they do not answer the phone, within two weeks of generation of the primary outcome data. They will be asked to verbally (or by email) consent to continue participation at that time. At least three attempts will be made to contact participants by a combination of the two techniques, phone or email. These attempts and the participants' responses will be documented in the source documents and electronic data capture system. As there is only a single visit at 12 months after signing the consent for the extension trial, no reconsent beyond this will be performed. This verbal/email reconsent possibility will be included in the original consent of the extension trial. Regardless of their treatment decision after learning the results of the primary DISCOMS trial, they will be followed to the end of the extension trial with the treatment as they choose in response to the primary results.

Primary endpoints will be defined as either:

1. "Relapse" will be defined as the appearance of new neurological symptoms or worsening of pre-existing neurological symptoms lasting at least 48 hours in a subject who had been neurologically stable or improving in the previous 30 days *and* accompanied by objective change in the neurological examination corresponding to that symptom (worsening of 0.5 point on the EDSS or worsening by 1.0 or more points on the pyramidal, cerebellar, brainstem or visual functional system score). Fatigue or subjective cognitive worsening, alone or in combination, will not be considered a "Protocol defined relapse."

Each Relapse event will be categorized on CRFs as one of the below:

• Protocol defined relapse

A relapse seen within 7 days of onset, independently and blindly observed as a change in EDSS by the Examining Clinician. This relapse is defined as: the appearance of a new symptom or worsening of an old symptom, attributable to MS; accompanied by a change in the neurologic examination attributed to those

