a. Aim #1: Proposed Data Analysis: We will perform an extension of the primary DISCOMS study, that being the time to failure defined as a protocol-defined disease event with each treatment group extending the understanding of the durability of the assigned treatment arm beyond the original DISCOMS follow-up period. A countable event will be a new protocol-defined relapse, and/or a new brain MRI lesion. We will estimate the long-term differences between the two treatment arms. Further by linking the time to event within the 100 participants with the original DISCOMS event free survival estimates, we can further evaluate the null hypothesis of inferiority with the proportion of disease events for the discontinue group being 0.08 proportion worse (our original noninferiority margin) at later time points of follow-up than the proportion for the continue group under the alternative that the two rates are equal. Because of the expected small numbers of events, we will use Kaplan-Meier estimates of the differences to obtain a confidence interval for comparing the proportions with individuals counted at their respective event times or censored based on their last known status. If the upper bound of the 95% confidence interval for the difference between the groups is less than 0.08, then we can reject inferiority and rule out discontinuation increasing the disease event proportion by 0.08 or greater. Our primary goal here is to estimate these differences given the relatively small sample size included, but we will calculate these values using the data obtained. In the unlikely event the proportions are relatively large, we will also calculate estimates and confidence intervals for relative risks. Larger numbers of events would permit the fitting of more complex models, but to date we know that the majority have not failed although their assignments are not known to us.

b. Aim #2: Proposed Data Analysis: We will calculate estimates and confidence intervals, using exact methods as necessary, for the proportion of disease events in both the discontinue and continue groups after this extension

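### Follow-up after a results-driven treatment change appears to stay in the assigned arm, and no persistent-exposure analysis checks the 0.08 non-inferiority reading

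*Combined protocol and SAP*

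**What the plan says.** **The question.** Section I states the main hypothesis for people who stopped DMT in DISCOMS and "remain off DMT after DISCOMS are at no greater risk of new or worsened MS disease activity" than those who stayed on it. The specific aims say that "we will compare clinically significant and patient-relevant outcomes in those who have persistently discontinued vs persistently continued DMTs". The inclusion criteria (III.B) add: "Must be willing to continue in their previously-assigned treatment group for the entire, additional 12-Month follow-up period". The Sample Size text in III.F explains that enrolling people who had left their assigned arm was considered and decided against.

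**What happens after disclosure.** Section III.D says DISCOMS results may become available before the extension ends. Participants still in the extension would then be told within two weeks and asked whether they wish to go on. Whatever they decide about treatment, "they will be followed to the end of the extension trial with the treatment as they choose". The same section leaves DMT choice to patient and physician throughout.

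**The analysis.** Under Aim 1 in III.F, the comparison is by assigned treatment arm, with Kaplan-Meier estimates and "individuals counted at their respective event times or censored based on their last known status". The extension data are linked to the DISCOMS event-free curve. Inferiority is rejected if the upper 95% bound for the difference is below 0.08.

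**The one rule on switchers.** Section III.C counts as failures those whose assignment changed between months 24 and 36 because of a relapse, a new MRI lesion or another MS-related reason. No section says how to analyse an event-free participant who changes treatment because of the disclosed results.

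**The concern.** The question is about persistent exposure, while the analysis appears to include follow-up under the other exposure. A discontinuer who restarts, or a continuer who stops, would go on contributing time to the arm that they have left. If discontinuation raises risk, both kinds of switch bring the arms closer together. In a superiority trial that is conservative. Under a non-inferiority rule it makes a no-worse conclusion easier to reach.

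The plan also treats the same behaviour in two ways. A person who finished DISCOMS and then changed assignment without an event before entering the extension is excluded (III.B, III.C). A person who makes the same change after entry, in response to the results, is kept and followed (III.D). At stake is whether a no-worse statement describes staying off therapy or only having once been assigned to stop it.

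**Working it through.** **1. Can disclosure fall within follow-up?** The Background (II) puts the last DISCOMS visit in August 2021, the month of this protocol version, and the last enrolment on 4 February 2020. With an 18-month final DISCOMS visit, Table 2 puts that participant's T1 at month 30, about August 2022. Results generated before then would reach people still under follow-up. Others will have finished: T0 and T1 may be the same day, and 49 of 123 completers (40%) were already at least 12 months past DISCOMS in December 2020 (III.C).

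**2. The plan's own figure.** The Sample Size text gives a one-sided Fisher p of 0.036 for 10/50 against 3/50. It reproduces (0.0357). It assumes no switching and does not bear on the rule at issue.

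**3. Dilution formula.** Observed excess = true excess × [1 − (f_D + f_C) × t]. Here f_D and f_C are the shares switching in each arm, and t is the share of the analysed time that follows the switch. Assumed, because the documents give no values: true excess 10 points, f from 20% to 40%, switch halfway through a 12-month extension, excess accruing evenly, and effect reversing at once.

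| Base | t | 20% in each arm | 40% in each arm | 20% in one arm | 40% in one arm |
|---|---|---|---|---|---|
| Extension only | 6/12 = 0.5 | 10 × (1 − 0.4 × 0.5) = 8.0 | 10 × (1 − 0.8 × 0.5) = 6.0 | 9.0 | 8.0 |
| Linked curve, T1 at month 36 | 6/36 = 0.167 | 10 × (1 − 0.4/6) = 9.3 | 10 × (1 − 0.8/6) = 8.7 | 9.7 | 9.3 |

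The linked base is less affected because entrants kept their assignment throughout DISCOMS. A T1 later than month 36 would raise t.

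**4. Which true excesses are pulled to the margin?** Divide 8 points by the retained fraction, for switching in both arms:
- Extension only: 8/0.8 = 10.0 points at 20%; 8/0.6 = 13.3 at 40%.
- Linked curve: 8/0.933 = 8.6 points at 20%; 8/0.867 = 9.2 at 40%.

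On the linked curve, then, only a true excess just above the margin would be expected to appear at or below it. The rule uses the upper confidence bound, which moves down roughly with the estimate.

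**5. Effect on the decision rule, extension alone.** Assume 50 per arm, true proportions of 14% and 6% (a difference equal to the margin), and 20% of each arm's risk spent on the other treatment. That share of risk corresponds to 40% of participants switching halfway. The proportions become 0.14 × 0.8 + 0.06 × 0.2 = 0.124 and 0.06 × 0.8 + 0.14 × 0.2 = 0.076, a difference of 0.048. By exact enumeration, the chance of wrongly rejecting inferiority rises from 4.3% to 10.9% with a Wald interval, or from 2.2% to 6.8% with a Newcombe interval. The linked curve was not computed, because its precision depends on DISCOMS data that the documents do not give.

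**The case against.** The strongest reply has five parts.

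- **Silence, not a rule.** III.D concerns follow-up and renewed consent, not analysis sets, and last known status in III.F is not defined with respect to treatment. A reader might infer that the plan expressly keeps switchers in their original arm. It does not. That reading comes from the reference to the assigned arm under Aim 1 and to maintained randomization under Aim 3. It is the natural reading, but it remains an inference.
- **Limited reach.** A reader might infer that every participant will learn the results. Disclosure is only a possibility, and it reaches only those still enrolled.
- **Partial cover.** The failure rule in III.C already handles changes made for MS-related reasons, and does so conservatively.
- **Small on the linked curve.** The 0.08 rule is applied to the linked curve, where the illustration loses about 0.7 to 1.3 points. Section III.E concedes too little power for non-inferiority in the extension alone, and Aim 1 calls estimation the primary goal.
- **A pragmatic trial.** Following people on the treatment that they choose is sound and answers a treatment-policy question.

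All five stand as limits on size and wording. They do not remove the mismatch: the stated hypothesis is about persistent exposure, the 0.08 rule is retained, and nothing prespecified shows whether switching influenced the answer. Low power does not excuse bias in the estimate itself.

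**Conclusion.** The point holds in a limited form. The plan asks about staying off or on DMT, allows treatment changes after disclosure, and, read as written, analyses the time after a change in the assigned arm. If discontinuing raises risk, the difference shrinks toward non-inferiority. If it does not, there is no such shrinkage. Switching related to prognosis could bias the result in either direction.

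For an assumed 10-point excess and 20% to 40% switching in each arm halfway through the extension, the expected excess is 8 to 6 points in the extension alone and about 9.3 to 8.7 on the linked curve. The switching shares are assumptions. Table 1 shows 17 of 42 continuers planning to stop and 6 of 42 discontinuers planning to restart, but such people are excluded at entry, so these are not forecasts. Equal switching in both arms and immediate reversal of effect both make the illustration larger than it might otherwise be.

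A reader might infer that a real 10-point excess would be reported at or below the margin. On the linked curve, to which the margin applies, these assumptions do not produce that.

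**What to change.** In III.F, Aim 1:

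1. Keep the as-followed analysis by assigned arm, and say that time after a switch remains in that arm.
2. Prespecify a second, persistent-exposure analysis that censors at the date of any change of assignment not related to MS activity. Concomitant medication is already collected (Table 2); add the reason for the change.
3. Keep changes that follow a relapse, a new lesion or another MS-related reason as failures, as III.C states, and say whether a results-driven change falls under that last phrase. Censoring every switch not preceded by a primary endpoint would conflict with III.C and could remove failures from the discontinue arm.
4. The only scheduled extension MRI is at T1, so a lesion seen there in a switcher cannot be placed before or after the switch. Report the persistent-exposure analysis with switchers' T1 lesions counted and not counted.
5. State that discontinuation is no worse against the 0.08 margin only if the as-followed and persistent-exposure analyses agree.

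The cost is one data field, one censoring rule and an extra analysis run in two variants. The second analysis loses some follow-up, and its censoring may be informative. For that reason it accompanies the as-followed analysis and does not replace it.

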- During the primary DISCOMS study, no evidence of recent new inflammatory disease activity (inactive by the Lublin criteria¹⁶). Pseudorelapses due to infection, fever, or other stressors as deemed by the local PI will NOT be excluded. Those who have already successfully completed the primary DISCOMS study without having a new relapse or MRI scan change, but who have a relapse or scan change AFTER ending participation in DISCOMS but before entering the extension ARE eligible and will be recruited, i.e. we do not wish to undercount new activity that occurs after exiting DISCOMS.
- Provides informed consent to continue in the extension trial.
- Willing to follow the protocol.

• Able to undergo a brain MRI without anesthesia, as part of routine care (i.e. paid for by their insurance). * Continuously will be defined as no less than 75% of all prescribed doses, with no time of greater than four weeks from last intended dose to have missed a dose (8 weeks for natalizumab, i.e. one missed dose).

Exclusion criteria:

- During original DISCOMS trial participant was randomized to the discontinue group, but then either restarted their DMT during the trial (study-defined 'treatment withdrawal), or wishes to restart their DMT after completing original DISCOMS study. Conversely, also excluded are those who completed the primary trial in the continue group and then discontinued, or wishes to discontinue, after completion of the primary study.
- Any MS relapse or new MRI scan lesion (3 mm or larger) during the primary DISCOMS trial, with relapse determined by the blinded examiner and MRI lesion determined by the blinded MRI reader.
- Significant (as defined by the PI) intolerance of presently-used DMT, if taking a DMT
- The following must **not** have occurred during the original DISCO MS study or since completing the study:
 - Use of any non-FDA-approved DMT
 - More than two courses of acute, systemic (IV or oral). Course is defined as three or more days continuously, and not to exceed 14 days. No use of chronic, systemic steroids, defined as 15 or more days. Any use of steroids to treat MS relapse, possible relapse, or pseudo-relapse is excluded. Inhaled or topical steroids for non-MS are not exclusionary.
 - Use of alemtuzumab, mitoxantrone, cyclophosphamide, methotrexate, cyclosporine, rituximab, or cladribine.
 - \circ $\,$ Use of any experimental agent used as a DMT for MS $\,$
 - Cancers other than basal cell skin cancers

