This will be a non-randomized, rater-blinded pragmatic trial, which is an extension of the randomized discontinuation trial (RDT)⁸², DISCOMS. While RDTs have been done in cancer^{83,84} and rheumatoid arthritis patients,⁶⁶ the original DISCOMS protocol was the first such study in MS. For this protocol, a subset of 100 subjects of the original 260 enrolled will be followed. Study sites will be limited to the top 10 recruiting sites across the United States from the DISCOMS study due to financial and cost-effectiveness issues. Those sites will have participants who have completed 18-24 months of the primary study. In practice, the vast majority, if not all, will have completed 24 months. We will explicitly include any who have completed, including those who already have exceeded 12 additional months after completion of the primary trial. Individuals who have successfully completed (retained original drug assignment and did not meet the primary endpoint of DISCOMS) the primary DISCOMS trial and are willing to retain their original drug assignment after completion and for an additional 12 months will be offered entry into the extension. The only exception to that will be individuals who continued the original drug assignment during and after the primary trial, up to 24 months, but who then had a relapse, new MRI lesion, or other MS-related reason between months 24 and 36 which resulted in their change of medication assignment. These individuals can and should be included, and counted as "failing" during the extension trial completing the Kaplan-Meier event free survival curve critical to the original hypothesis. A total of up to 100 patients will be consented and enter the extension trial, regardless of assignment, on a first come first serve basis to avoid selection biases to the extent possible. The intent is to take the first 100 who fulfill criteria and agree to participate. The plan is for a 50/50 distribution, but there may not be exactly 50 in each group. As of December 15, 2020, 123 had completed participation of the primary 24-month study, and information as to DMT use plans after finishing 2-years participation in DISCOMS was available for 84/123, 42 in each group (see Table 1 below). Notably, in the Discontinue group, 86% remained off DMT while only 60% in the Continue group plan to remain on a DMT (23/42 on the same DMT, two switching to an alternative). Overall 73% remained in the primary assignment grouping. If these ratios stay consistent as more finish DISCOMS, discontinuers will account for roughly 59% of the total enrolled in the extension trial. Also, of the 123 completers, 49 have also gone at least an additional 12 months since completion of DISCOMS, and they will be offered entry into the extension trial, should they otherwise fulfill criteria. There will be no placebo and no sham treatment. (Please see the statistics section the extension ns for power analyses discussions).

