symptoms (defined as worsening of 0.5 point on the EDSS or worsening by 1.0 or more points on the pyramidal, cerebellar, brainstem or visual functional system scores); symptoms lasting at least 48 hours in the absence of fever; and preceded by stability or improvement for at least 30 days. Any use of systemic steroids to treat MS symptoms will be counted as a Protocol defined relapse, regardless of when the patient was seen.

• Out of window relapse

Same as a protocol defined relapse, except that the patient was not seen within the 7-day window.

• Suspected relapse

Relapse that fails to meet the above situations, but may have been a relapse –i.e. all circumstances point to a relapse, but upon examination by the examining physician, no residual or change in the EDSS is noted.

Not a Relapse

Pseudo-relapse, i.e. a worsening of pre-existing neurological symptoms in the context of any significant stressor, including, but not limited to, infection, or physical, psychological or mental stress, as determined by the treating physician; or other symptoms felt not to be related to MS.

For the primary outcome, we will use Protocol defined relapse for analysis, with secondary analyses combining this with Out of window and Suspected relapses. For the above categorization, it is imperative that the subject be seen at time of relapse. Once the patient feels that they have experienced a relapse, the patient needs to contact the PI and study coordinator as soon as possible. Patients need to be seen at the clinic ideally within 1-3 days, and within 7 days at the latest, of onset of symptoms or the relapse will not qualify as a Protocol defined relapse. If the patient is unable to identify whether he/she is experiencing a relapse and does not contact the clinic to be seen within 7 days, it does not qualify as a Protocol defined relapse. When subjects are not scheduled for a clinic visit, the coordinators will call them once at the 30 month time period to assess potential relapses. The purpose of this phone call is to determine whether the patient is experiencing a relapse, or has experienced a relapse since the last clinic visit or phone call. As with scheduled visits, at an unscheduled visit the Examining Clinician will determine if a relapse occurred based on the EDSS evaluation, and a post-EDSS review of the presenting symptoms.

Or

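### Section III.C counts failures that the primary endpoint does not, and the steroid exclusion can remove people whose relapse the endpoint would count

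*Combined protocol and SAP*

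**What the plan says.** **Counting.** Section III.D gives the primary endpoint two parts: a Protocol defined relapse, or a new or clearly enlarging T2 brain lesion of at least 3 mm. A Protocol defined relapse must be seen within 7 days of onset, with a change on the EDSS or a functional system score found by the blinded examiner. Any MS symptoms treated with systemic steroids also count, whenever the patient was seen. On the other relapse categories III.D says: "For the primary outcome, we will use Protocol defined relapse for analysis, with secondary analyses combining this with Out of window and Suspected relapses". The Aim 1 text in III.F repeats the two-part event.

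Section III.C makes an exception to its rule that participants keep their assigned treatment. It covers people with a "relapse, new MRI lesion, or other MS-related reason between months 24 and 36 which resulted in their change of medication assignment", and continues "These individuals can and should be included, and counted as" failing on the Kaplan-Meier curve. Later in III.C the exception is restated for a relapse or new MRI lesion only, subject to verification of the event. No standard of verification is given.

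**Eligibility.** The III.B inclusion list covers people who completed DISCOMS without an event "but who have a relapse or scan change AFTER ending participation in DISCOMS but before entering the extension ARE eligible and will be recruited". The reason given is that "we do not wish to undercount new activity that occurs after exiting DISCOMS". The III.B exclusion list names things that must not "have occurred during the original DISCO MS study or since completing the study". One of them is any steroid use for an MS relapse, possible relapse or pseudo-relapse. The treatment-retention bullets require "Randomized to the discontinue group, stayed off their DMT throughout and after the trial" and allow continue-group switches "but NOT if due to having new or worsening MS disease activity".

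**The concern.** The Aim 1 analysis needs one rule for what ends event-free time. The plan has two, and they disagree for people whose event fell between leaving DISCOMS and signing the extension consent (below, the gap). An analyst working from III.C and one working from III.D and III.F would code some of the same people differently.

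The eligibility text adds a second problem. Steroid treatment is the one route by which a relapse not seen in time becomes a primary event. Steroid treatment since DISCOMS is also a reason for exclusion. Followed as written, the plan can remove a person because of the event it sets out to count. At stake are the event proportions in each arm, their difference, and the interval that Aim 1 compares with the 0.08 margin.

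**Working it through.** **Step 1: apply each rule to the same person.** All four people have the event in the gap.

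| Event in the gap | III.C | III.D and Aim 1 | III.B |
|---|---|---|---|
| Relapse without steroids, no new lesion, medication changed | Failing | Normally secondary analyses only | Eligible, reading III.C as overriding the retention bullets |
| Relapse treated with steroids | Failing if medication changed | Primary event | Called eligible, but excluded by the steroid criterion |
| Medication changed for another MS-related reason, no relapse or lesion | Failing (absent from the restatement) | No event category | Admitted only through the III.C exception |
| New qualifying brain lesion | Failing if medication changed | Primary event | Eligible |

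Rows 1 and 3 are the counting conflict. Row 2 is the eligibility conflict; the III.C exception concerns changes of medication and does not mention steroids. Row 4 shows no conflict.

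Row 1 follows because no extension visit takes place before consent. Late enrollees get the equivalent of the phone assessment at T0, and everyone gets a blinded relapse assessment at T1. For a gap relapse both look back in time, so they cannot supply an examination within 7 days of onset.

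**Step 2: how many people have a gap.** Section III.C reports that on 15 December 2020, 49 of 123 completers were at least 12 months past DISCOMS: 49/123 = 0.398, or 40%. For those who enrol, T0 and T1 can be the same day (III.C, Table 2), so their events would be established retrospectively. This counts people before eligibility limits, not relapses.

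**Step 3: reproduce the plan's figure.** The Sample Size text takes 10 of 50 discontinue and 3 of 50 continue failures. One-sided Fisher exact: p = sum over x from 10 to 13 of C(50,x)·C(50,13−x)/C(100,13) = 0.0357. The stated 0.036 is reproduced.

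**Step 4: direction when an event is lost.** Wald upper bound at 50 per arm: d + 1.96·sqrt[p1(1−p1)/50 + p2(1−p2)/50].

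| Events (discontinue v continue) | Difference d | Upper bound | One-sided p |
|---|---|---|---|
| 10 v 3 | 0.14 | 0.269 | 0.036 |
| 9 v 3 | 0.12 | 0.245 | 0.061 |
| 10 v 2 | 0.16 | 0.284 | 0.014 |

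Losing one event lowers or raises the difference, depending on the arm. All three bounds exceed 0.08.

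**Step 5: sensitivity of the linked curve.** Assumptions: 130 per arm at risk in DISCOMS (260 enrolled 1:1), then 50 per arm; the same 24-month event-free proportion S24 in both arms; k extension events. Then S = S24·(1 − k/50), with variance S²·[((1−S24)/S24)/130 + (k/(50−k))/50]. The upper bound is the difference plus 1.96 times the root of the summed variances.

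With S24 = 0.95 and 2 v 2 events, S = 0.912, each variance is 0.00103 and the bound is 0.089. With 1 v 1, S = 0.931, each variance is 0.000705 and the bound is 0.074. Across S24 of 0.90, 0.92, 0.95 and 0.98 and equal counts from 0 to 4, 4 of 16 one-per-arm steps cross 0.08 and 12 do not.

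Halving unequal counts at S24 = 0.95 takes 4 v 2 to 2 v 1 and lowers the bound from 0.139 to 0.101. At S24 = 0.90, 2 v 4 to 1 v 2 raises it from 0.072 to 0.075. S24 and the event counts are not in the documents, so this shows sensitivity, not expected size.

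**The case against.** Several points on the other side carry weight.

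- **The primary definition is already chosen.** III.D states which relapses are primary and which are secondary, and III.E stresses blinding. A reader might infer that the plan leaves this open; it does not. What stands is that III.C counts people that definition does not.
- **The retention bullets.** A reader might infer that they bar everyone who changed treatment after a relapse. III.C presents its exception as the only departure from the retention rule, so it can be read as overriding them. Their silence about the exception is a minor alignment point.
- **The steroid sentence.** It might be read as leaving relapse courses out of the two-course limit. The next sentence, under which inhaled or topical steroids do not exclude a person, makes exclusion of the person the natural reading.
- **Dates.** The adverse event form in III.D records start and end dates, so a source exists. Adverse events are defined as arising after the study starts, so cover for the gap is arguable.
- **Limited reach.** Participants who roll over at Month 24 have no gap. The T1 MRI captures relapses that leave a qualifying lesion. III.E concedes insufficient power for non-inferiority, and Aim 1 makes estimation its main goal. This lowers the stakes for the 0.08 test but not for the estimates.

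**Conclusion.** Two contradictions stand. Section III.C counts as failures some people whom III.D and Aim 1 do not. Section III.B invites people who relapse after DISCOMS, then excludes those treated with steroids, whose relapse III.D would count as primary. The plan should be corrected on both.

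The effect is on the Aim 1 event proportions, their difference and its interval. Its size cannot be given, because the documents state no rate of gap relapses.

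A reader might infer that lost events push the result towards showing discontinuation to be no worse. The documents do not support this: the direction depends on how the losses split between arms, and moving from 10 v 3 to 10 v 2 widens the difference from 0.14 to 0.16. Nor do they support saying that the 0.08 conclusion would flip, since the crossings in Step 5 rest on assumed counts. The 40% is not a share of relapses missed.

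**What to change.** Before results are seen:

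1. Reconcile III.B, III.C, III.D and the Aim 1 text into one failure definition. Drop the unspecified MS-related reason as a primary failure, keep and follow those people, and state their censoring rule.
2. Reconcile the III.B steroid exclusion with the III.B eligibility sentence and the III.D endpoint rule, so that a relapse after DISCOMS does not itself remove the person. Carry the III.C exception into the retention bullets. No view is taken here on steroid or DMT management.
3. Keep the Protocol defined relapse as primary. Add one Aim 1 Kaplan-Meier sensitivity run that includes gap relapses verified by the blinded Examining Clinician from available records with treatment redacted, dated at onset.

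The cost is protocol and analysis wording, one extra run, and retrieval and redaction of records for participants who report a gap relapse. No visits or participants are added. The drawback is that these relapses are less standardised and were first documented by unblinded clinicians, which is why they belong in a sensitivity analysis.
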